6.6.2 Safety Labs

Summaries and analyses of clinical safety labs are the same as specified in the M-SAP with the revision that abnormal levels will be classified to a toxicity grade based on quantitative grading using National Cancer Institute (NCI) Common Terminology Criteria for Adverse Events (CTCAE) version 5.0 and with the addition that maximum toxicity over all post-baseline visits will be included in shift tables along with visit-specific shifts.

Potential drug-induced liver injury (DILI), including cases that potentially meet the Hy's law criteria, will be reported as distinct safety lab outcomes. Three potential DILI criteria will be defined:

- ALT or AST >3xULN with TBL >1.5xULN
- AST or ALT >3xULN with TBL >2xULN
- AST or ALT >3xULN with TBL >2xULN and ALP <2xULN (potential Hy's Law cases)

where ALT is alanine transaminase level, AST is aspartate transaminase level, TBL is total bilirubin level, ALP is alkaline phosphatase level, ULN is upper level of normal, and all levels are measured on the same day.

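### The potential liver-injury criteria pair transaminases and bilirubin only within one day, so a bilirubin rise first seen after ALT and AST are back to 3xULN or below is not flagged

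*SAP*

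**What the plan says.** SAP 6.6.2 Safety Labs adds a liver outcome to the default laboratory summaries: "Potential drug-induced liver injury (DILI), including cases that potentially meet the Hy's law criteria, will be reported as distinct safety lab outcomes". There are three criteria:

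- Criterion 1: "ALT or AST >3xULN with TBL >1.5xULN".
- Criterion 2: "AST or ALT >3xULN with TBL >2xULN".
- Criterion 3: the same as criterion 2, with ALP also below 2xULN. This is the one labelled as potential Hy's law.

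The definitions end with the timing condition "and all levels are measured on the same day", which applies to all three. ALP enters only criterion 3. No rule is given for combining results from different days.

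Elsewhere in the same section, toxicity grades are summarised across visits: "maximum toxicity over all post-baseline visits will be included in shift tables along with visit-specific shifts". Everything else defers to the master plan: "Summaries and analyses of clinical safety labs are the same as specified in the M-SAP". That plan (M-SAP) was not available for this review. SAP section 1 says the regimen SAP prevails where the two differ.

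**The concern.** The criteria are meant to pick out potential cases, so sensitivity matters more than specificity. An extra flagged participant costs one review. A missed one is absent from the only table that links the two elevations.

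With same-day pairing, the result depends on whether a single draw catches both elevations. If ALT or AST is high on one draw with bilirubin still below threshold, and bilirubin is high on the next draw after the transaminases have fallen, no criterion is met. The shift tables would show both abnormalities, but analyte by analyte, so they would not identify one participant with both.

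The documents give some reason to want this table complete. Protocol 1.1.2 states that pridopidine has not been studied in hepatic impairment, and Protocol 5.11.1 states that there is no earlier experience in ALS. About 120 participants are planned for active treatment (RSA Summary), so few liver cases of any kind should be expected and each would be read individually.

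**Working it through.** The plan states no figure to reproduce. The check is of the rule's logic, followed by draw spacing.

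**Notation.** At draw k, let A be the larger of ALT and AST, B be TBL and P be ALP, all in multiples of ULN. The TBL threshold c is 1.5 for criterion 1 and 2 for criteria 2 and 3.

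- Rule as written: some draw k has A(k) > 3 and B(k) > c; criterion 3 also needs P(k) < 2.
- Across-day rule: some draw k has A(k) > 3, and some draw m, the same or later, has B(m) > c; criterion 3 also needs P(k) < 2.

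Every same-day case also satisfies the across-day rule (take m = k), so the second count can only equal or exceed the first.

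**Hypothetical sequences** (values chosen for illustration):

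| Sequence | As written, criteria 1/2/3 | Across-day, criteria 1/2/3 |
|---|---|---|
| A: ALT 10, TBL 1, ALP 0.9; then ALT 4, TBL 2.5, ALP 1 | yes/yes/yes | yes/yes/yes |
| B: ALT 10, TBL 1, ALP 0.9; then ALT 2, TBL 2.5, ALP 1 | no/no/no | yes/yes/yes |
| C: ALT 10, TBL 2.5, ALP missing | yes/yes/no | yes/yes/no |
| D: ALT 10, TBL 2.5, ALP 2.5 | yes/yes/no | yes/yes/no |

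A and B both have bilirubin rising after the transaminase peak. Only B is missed, because ALT is at or below 3xULN when TBL is high. C and D confirm that ALP affects criterion 3 alone.

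**Draw spacing** (SAP 2.9; safety labs at Day 28, 56, 112 and 168, each ±7 days):

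- Week 4 to Week 8: 56 − 28 = 28 days; with windows, 28 ± 14, or 14 to 42 days.
- Week 8 to Week 16: 112 − 56 = 56 days; with windows, 56 ± 14, or 42 to 70 days.
- Week 16 to Week 24: 168 − 112 = 56 days; again 42 to 70 days.

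**Time above 3xULN.** Assume ALT falls exponentially from its peak with half-life h. The days above 3xULN are h × log2(peak/3). For a peak of 10 and h = 5, this is 5 × log2(3.33) = 5 × 1.737 = 8.7 days. Peaks and half-lives are assumptions; the documents give neither.

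| Peak (xULN) | h = 2 days | h = 5 | h = 10 | h = 20 |
|---|---|---|---|---|
| 5 | 1.5 | 3.7 | 7.4 | 14.7 |
| 10 | 3.5 | 8.7 | 17.4 | 34.7 |
| 20 | 5.5 | 13.7 | 27.4 | 54.7 |
| 40 | 7.5 | 18.7 | 37.4 | 74.7 |

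If the peak falls on a scheduled draw, ALT is at or below 3xULN by a draw 28 days later in 12 of these 16 cells, and by a draw 56 days later in 15 of 16. These are not probabilities of a missed case. Bilirubin must also be above threshold on the later draw and not on the earlier one. They show only that the schedule can separate the two elevations over most of the range examined.

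**The case against.** A reader might infer three stronger things from the same-day clause, and the documents support none of them.

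- That every criterion needs a same-day ALP. Only the third has an ALP term.
- That any bilirubin rise following the transaminase peak is lost. The clause asks only that ALT or AST still be above 3xULN on the day TBL is high; sequence A meets all three criteria.
- That participants are put at risk. Section 6.6.2 defines reported outcomes and nothing in it directs care. SAP section 1 leaves matters other than analysis to the Master Protocol and the RSA, and adverse events are reviewed at every visit.

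Several further objections carry weight. Same-day or across-day pairing is a choice of definition, and same-day pairing is less likely to join unrelated abnormalities. The use of maximum grades in the shift tables is not an inconsistency: those grade one analyte at a time, while the liver criteria are joint conditions. The RSA discusses QT prolongation as the known potential risk and reports no hepatic signal. No number of missed participants can be derived, nor can any effect on the overall safety conclusion. The M-SAP may already contain a peak-against-peak display or a listing.

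What remains is narrow but firm. The clause is explicit and no cross-day rule sits beside it. If the M-SAP has a different one for these criteria, the regimen SAP overrides it.

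**Conclusion.** The point holds as a cheap improvement. For each criterion, the rule omits participants whose TBL is above threshold only on draws where neither ALT nor AST exceeds 3xULN. Someone with TBL between 1.5 and 2xULN at the ALT elevation and above 2xULN only later would meet criterion 1 but miss criteria 2 and 3.

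The size is unknown and may be zero. That the omission can occur follows from the definition and the visit schedule alone. How often it occurs depends on peaks, clearance and bilirubin timing that the documents do not give. Neither efficacy analyses nor participant management is affected.

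**What to change.** Amend SAP 6.6.2, for analysis and reporting only:

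- Keep the three same-day counts as they are.
- Beside each, add a count of participants with ALT or AST above 3xULN and TBL above that criterion's threshold on the same or a later post-baseline draw. For criterion 3, take ALP at the ALT/AST elevation.
- Either use all post-baseline draws or state a window. A window must reach about 70 days to link consecutive scheduled draws. One of 30 days, for example, could never link Week 8 to Week 16 or Week 16 to Week 24, which are at least 42 days apart. If the Week 16 draw is missed, Week 8 to Week 24 spans 112 ± 14, or 98 to 126 days, which favours using all post-baseline draws.
- Add a plot of each participant's peak ALT/AST against peak TBL, unless the M-SAP already provides one. It needs no window.

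The cost is a sentence or two of SAP text, a small derivation change and possibly one figure, all from data already collected. The across-day count will list some additional participants, a few with unrelated elevations. Showing it next to the same-day count lets the reader see how many the wider pairing adds.

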6.6.3 ECG Results

Summaries of ECG parameters and findings are the same as specified in the M-SAP with the additional of summaries of the proportion of participants meeting ECG stopping rules or meeting ECG monitoring rules 1, 2, or 3 times.

6.6.4 Vital Signs and Weight

Summaries and analyses of vital signs and weight are the same as specified in the M-SAP.

6.6.5 Suicidality

Summaries of suicidality are the same as specified in the M-SAP.

6.7 Other Analyses

6.7.1 Participant Disposition

All participants consented to the Master Protocol between the time of the first and last consent of a participant assigned to a regimen included in the FAS analysis set will be summarized as a single set for the following events: consented to the Master Protocol, failed screening for the Master Protocol, other reasons not assigned to a regimen (including timing out of the screening window, death, withdrawal of consent, early termination, and administrative termination), and assigned to a regimen. Reasons for Master Protocol screen failure will be summarized.

All participants in the above sample assigned to a regimen will be summarized as two sets (final screening for RGD vs. final screening for a non-RGD regimen) for the following events: consented to a regimen, failed screening for a regimen, other reasons not randomized within a regimen (including timing out of the screening window, death, withdrawal of consent, early termination, and administrative termination), and randomized within a regimen. If a given individual is screened multiple times prior to randomization within a regimen, then the final screening experience of that individual will be summarized. Reasons for RGD screen failure will be summarized separately for all participants screened for RGD whether that was their final screening experience or not.

All participants in the FAS analysis set will be summarized as two sets (randomization to active study drug vs. randomization to placebo) for the following events: initiated regimen-specific study drug, prematurely terminated study participation due to death, withdrawal of consent, early termination, loss to follow-up, or administrative termination, completed 24-week follow up, and completed a safety follow-up visit vs. continued into the OLE. Reasons for withdrawal of consent or early termination after randomization will be summarized.

6.7.2 Study Drug Compliance and Tolerance

Summaries of study drug compliance and tolerance are the same as specified in the M-SAP with the clarification that summaries will be reported for the ERO and SRO analysis sets and that date of permanent discontinuation of study drug is the date of last use of double-blind study drug among all participants in a given analysis set. The number of days of exposure to study drug will be calculated as the number of days from dose initiation to drug withdrawal, inclusive, less any day(s) during which use of study drug was interrupted. The proportion of participants who interrupted study drug or reduced study drug dosage and the time to first study drug interruption or dosage reduction will be summarized. The number of days of exposure to a reduced dosage of study drug will be summarized.

6.7.3 Concomitant Medication Use

Summaries of concomitant medication use are the same as specified in the M-SAP with the clarification that medications taken at baseline and those initiated after first dose of study drug will be separately summarized and will be classified by ATC Therapeutic class and WHODrug Preferred base name.

6.7.4 Medical History

Medical histories will be summarized by MedDRA system organ class, high level term, and preferred term in the STF and SRO analysis sets.

6.7.5 Blindedness

The proportions of participants and site investigators who report on the Exit Questionnaire a guess of active vs. placebo treatment assignment, each level of surety of that guess, and each of five pre-specified reasons for making a treatment assignment will be summarized by treatment group in the FAS and ERO analysis sets. Treatment-dependent differences in the proportion guessing active treatment assignment will be tested among all respondents and among those stating they are at least somewhat sure of their guess by Fisher's exact test and the difference in proportion guessing active treatment assignment will be estimated with confidence bounds.

6.7.6 Impact of COVID-19 Pandemic

The proportions of planned assessments missed due to COVID-19 restrictions or disruptions will be summarized by treatment group, visit, and type of assessment in the FAS and ERO analysis sets. Protocol deviations that resulted from COVID-19 restrictions or disruptions will be summarized by treatment group and type of deviation in the FAS and ERO analysis sets and listed.

7. Validation

7.1 Primary Efficacy Analysis

Validation of the primary efficacy analysis is the same as specified in the M-SAP.

